10.12.1 Efficacy Analyses

Primary Endpoint: The primary efficacy endpoint is linear healing rate (LHR) from TV1 to EOT as compared with LHR from RV1 to TV1. LHRs will be measured by a blinded wound expert using digital images at RV1, TV1, and EOT.

Within treatment groups, treatment phase will be compared to run-in phase by paired non-parametric test (Wilcoxon signed rank). Effects will be compared between groups using non-paired non-parametric tests (Mann-Whitney).

Secondary Endpoints:

Weekly LHR shall be compared as above.

EOT healing status between groups shall be compared by Mann-Whitney U test on the PWAT scores. Weekly LHR can be tested using the same method (and same wording) as final LHR. Incidence of healing shall be compared between groups using Fisher's exact test.

Intra-group pain reduction measured on a visual analogue scale (VAS) will be analysed using paired t-test.

Inter group differences in time to clinically significant reduction in VAS shall be tested using Mann-Whitney u-test.

Intra-group changes to both Quality of Life (QoL) instruments in the study (CWIS and EQ-5D-5L) shall be tested using Wilcoxon signed rank test.

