
Secondary Efficacy
 
The overall secondary efficacy endpoints are:
 
 • Weekly LHR of the study ulcer measured by an independent blinded wound expert using digital images taken at each weekly visit until EOT. • Wound healing status at baseline and EOT assessed by an independent blinded wound expert using the Photographic Wound assessment Tool (PWAT) to evaluate digital images taken at RV1, TV1 and EOT and at HCV, if scheduled. • Incidence of healing at EOT, as determined by the by the PI or designee. 
The participant reported secondary efficacy endpoints are:
 
 • Time from TV1 to clinically significant pain reduction measured using a Visual Analogue Scale (VAS) instrument. For the purpose of this protocol a clinically significant reduction of pain is a mean reduction of ≥ 20.65 mm or a mean decrease of $\geq 10-20\%$ in pain as measured on a 0-100 mm VAS. • Time from TV1 to first instance of no study ulcer pain measured using VAS. (No pain = < 5mm on VAS when VAS scores: 0-4 mm = no pain; 5-44 mm = mild pain; 45-74 mm = moderate pain; and 75-100 mm = severe pain) (1). • Pain score at EOT measured using VAS • Change from TV1 in Quality of Life (QoL) at EOT, assessed using the Cardiff Wound Impact Schedule (CWIS) • Change from TV1 in QoL at EOT, assessed using EQ-5D-5L 
 • Wound closure as reported by participants during the Follow-up Phase (FP1-FP3) 	

Safety Assessments
 
Safety will be assessed using the following parameters:
 
 • Incidence of AEs • Incidence of SAEs • Incidence of study ulcer infection • Incidence of study treatment related AEs (including geko™, compression bandaging and any dressings used to treat the study wound) • Incidence of investigational device (geko™) related AEs • Pain in the ulcer site (sudden onset of pain or increase in pain during the study Treatment Phase) 	

Trial Design: This study is designed as a prospective, multicentre, randomised, assessor blinded study designed to compare the efficacy, including participant reported outcomes, of a geko™ treatment in
	

Name of Sponsor/Company: Firstkind Ltd, [name]	
Name of Study Product: geko™ neuromuscular stimulator	

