2.1.2 Secondary Efficacy Endpoints

The secondary efficacy endpoints are:

- Weekly LHR measured by an independent blinded wound expert using digital images taken at each weekly visit until TV5, withdrawal or healing whichever comes sooner.
- Wound healing status at baseline and EOT assessed by an independent blinded wound expert using PWAT to evaluate digital images taken at RV1, TV1 and at withdrawal, healing or at the end of the Treatment Phase (TV5), whichever comes sooner.
- Incidence of healing at EOT, as determined by the Investigator

“Healing” of the study ulcer is determined by the PI or designee. “Healing” is defined as 100% re-epithelialised without drainage as confirmed at the Healing Confirmation visit (HCV).

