4.2 Treatment Phase

4.2.1 Treatment Visit 1 (TV1) – Prior to Randomization

The assessments on TV1 should be performed in the following order:

- Administer the CWIS and EQ-5D-5L questionnaires in the participant's primary language.
- Administer the study ulcer pain VAS assessment.

- Check for any changes in the participant's health. Any AEs during TV1 prior to randomisation are recorded in the participant's medical history. Following randomisation and during TV2-TV5, update the AE or Serious Adverse Events (SAE) CRF pages as applicable.
- Assess concomitant medications.
- Assess compression bandaging (See Section 9.8)
- Clean the study ulcer.
- Obtain a digital image of the study ulcer (if debridement is planned, this is the Pre-debridement image). N.B. All study ulcer measurements will be performed using the pre-debridement images.
- At the discretion of the Investigator, debride the study ulcer to obtain a clean, granulating ulcer base with minimal adherent slough.
- If applicable, obtain a post-debridement digital image of the study ulcer.
- Verify the participant's continued eligibility (See Sections 3.1.2 and 3.1.3).

If the participant is not eligible, discharge the participant from the study as a screen failure.

If a patient initially fails to meet inclusion/exclusion criteria he/she may later be reconsidered for participation, in which case the patient will be re-consented and assigned a new screening number at the time of re-screening. Patients who fail their first screening attempt may be re-screened once (i.e., up to two screenings) and be enrolled if they meet ALL inclusion and NO exclusion criteria at the second screening visit.

If the patient is eligible, perform the following procedures immediately

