10.7 Description of Study Endpoints

10.7.1 Primary Efficacy Endpoint

The primary efficacy endpoint for the study is LHR from TV1 to EOT as compared with LHR from RV1 to TV1. LHRs will be measured by a blinded wound expert using digital images at RV1, TV1, EOT, and at HCV if scheduled.

Each participant will be used as his/her own control, i.e. a participant's healing trajectory before commencement of treatment will be compared to his/her healing trajectory after introduction of treatment.

Since significant non-homogeneity may be expected in VLU participants and their respective healing trajectories, a pre-treatment run-in phase will be used to allow each participant to be used as his/her own control, i.e. a participant's healing trajectory before introduction of treatment will be compared to his/her healing trajectory after introduction of treatment. This allows an intra-group pair-wise comparison to evaluate the efficacy of each treatment regimen.

Additionally, for each participant, it enables generation of a treatment healing rate normalised relative to an initial healing rate. Inter-group (albeit un-paired) comparisons based on this normalised value are likely to be more sensitive than comparison of raw healing rates.

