10.7.2 Secondary Efficacy Endpoints

The secondary efficacy endpoints are:

- Weekly LHR measured by an independent blinded wound expert using digital images taken at each weekly visit until EOT.
- Wound healing status at baseline and EOT assessed by an independent blinded wound expert using PWAT to evaluate digital images taken at RV1, TV1, EOS, and at HCV, if scheduled.
- Incidence of healing at end of study, as determined by the Investigator

"Healing" of the study ulcer is determined by the PI or designee. "Healing" is defined as 100% re-epithelialised without drainage as confirmed at the Healing Confirmation visit (HCV).

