10.12 Analysis Methods

A SAP will be developed and approved before the database is locked. The SAP will present the detailed statistical methodology to be used in analysing the efficacy and safety data from this study.

All statistical tests will be two-sided and a 0.05% significance level maintained throughout the analyses.

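### The between-arm PWAT test ignores the TV1 score already collected, which costs precision on a secondary endpoint but does not bias it

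*Combined protocol and SAP*

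**What the plan says.** Section 10.12.1 states the whole PWAT analysis in one sentence: "EOT healing status between groups shall be compared by Mann-Whitney U test on the PWAT scores". It names no covariate, change score or stratification. ANCOVA is in the abbreviation list but in no analysis.

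The endpoint covers more than the end score. Section 10.7.2 words it as "Wound healing status at baseline and EOT assessed by an independent blinded wound expert using PWAT". The synopsis has the expert use PWAT "to evaluate digital images taken at RV1, TV1 and EOT and at HCV, if scheduled", and section 2.1.2 also lists RV1 and TV1. Section 10.7.2 writes EOS for the final time point ("using PWAT to evaluate digital images taken at RV1, TV1, EOS, and at HCV, if scheduled") where the other two point to EOT. The labels should be aligned, but all three places include TV1.

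Section 4.2.1 requires a study ulcer image from every participant at TV1 before randomisation. Under section 10.4 the expert receives images without participant or visit data. TV1 PWAT is therefore a true pre-randomisation covariate, scored blind.

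For linear healing rate (LHR), section 10.7.1 relates each patient's treatment rate to his or her own run-in rate and says that between-group "comparisons based on this normalised value are likely to be more sensitive than comparison of raw healing rates". That reasoning is not carried over to PWAT.

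Sections 10.1 and 10.12 leave detailed methods to a separate SAP.

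**The concern.** Patients enter the Treatment Phase with ulcers in different states, and section 10.7.1 itself expects marked heterogeneity. If TV1 PWAT predicts EOT PWAT, a test on EOT scores alone counts that predictable spread as noise. In a trial of 60 this matters in two ways: a real difference is more likely to be missed, and a chance difference between arms at TV1 shows up in part as an apparent difference at EOT. The value that would deal with both is already being recorded.

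**Working it through.** **The plan's own figures.** None concerns PWAT: there is no SD, effect size, correlation or power for it. The only current calculation is in section 10.5.2, for the within-group LHR comparison: 0.58/0.97 = 0.598, 80% power, two-sided 0.05, n = 25. A paired t calculation gives 24 (power at 25 is 81.8%), so the figure reproduces closely, but it says nothing about PWAT.

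**Inputs.**
- 60 randomised (section 3.1.1). The current allocation ratio is not stated, so 30 per arm is assumed.
- Loss of up to 20% (section 10.2, written for the 126-patient, three-group plan). If it applied, 30 × 0.8 = 24 per arm.
- Two-sided 5%, as in section 10.5.2. Section 10.12 prints "All statistical tests will be two-sided and a 0.05% significance level maintained throughout the analyses", which conflicts with 0.05 and should be reconciled.
- Assumed: rho = 0.3, 0.5 or 0.7, and a between-arm difference of 0.6 SD.

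**Precision.** Adjustment for TV1 multiplies the variance of the between-arm contrast by 1 − rho², equivalent to multiplying the patients by 1/(1 − rho²). The standardised effect becomes 0.6/√(1 − rho²). Power is from the two-sample t test, with noncentrality equal to the effect times √(n/2); the one degree of freedom spent on the covariate is ignored.

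| rho | Variance kept | Variance cut | Patients multiplied by | 30 per arm acts as | Effect used | Power, 30 per arm | Power, 24 per arm |
|---|---|---|---|---|---|---|---|
| unadjusted | 1.00 | – | 1.00 | 30 | 0.600 | 62.8% | 53.0% |
| 0.3 | 0.91 | 9% | 1.10 | 33 | 0.629 | 66.8% | 56.9% |
| 0.5 | 0.75 | 25% | 1.33 | 40 | 0.693 | 75.1% | 65.2% |
| 0.7 | 0.51 | 49% | 1.96 | 59 | 0.840 | 89.2% | 81.3% |

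**Chance imbalance.** Under simple randomisation with 30 per arm, the TV1 difference between arms has SD √(2/30) = 0.26 baseline SDs. It exceeds 0.25 SD with probability 33% and 0.5 SD with probability 5%. About rho times the difference reaches the EOT comparison: an imbalance of 0.25 SD contributes 0.075, 0.125 or 0.175 SD at rho = 0.3, 0.5 or 0.7.

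**Check with the actual tests.** The table is normal-theory, so the planned and proposed tests were also simulated on an integer 0–24 score (six PWAT domains of 0–4, Appendix 2), with 30 per arm, a 0.74 SD difference and 4,000 runs per setting.

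| rho | Mann-Whitney on EOT | Rank ANCOVA on TV1 | Mann-Whitney on change |
|---|---|---|---|
| 0.3 | 77.8% | 81.1% | 63.4% |
| 0.5 | 78.7% | 86.9% | 76.9% |
| 0.7 | 77.0% | 96.0% | 93.9% |

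With no true difference, all three rejected in 4.6–5.2% of runs. The planned test keeps its error rate, and so does the proposed one.

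**Change score.** With equal SDs its variance is 2(1 − rho) times that of the EOT score: 1.4, 1.0 and 0.6 at the three values. Below rho = 0.5 it is worse than ignoring TV1, as the first simulation row shows.

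**The case against.** The strongest reply is that nothing here is invalid. The Mann-Whitney test holds its level, PWAT is secondary, the trial is not powered on it, and detail is left to the SAP. This stands as a limit on the point, not as an answer to it: the protocol already names an unadjusted test, and a promised SAP does not change that.

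The gain may also be small. Rho is unknown and could be low. EOT can be the visit at which closure is first determined, and a closed ulcer falls towards zero on several PWAT domains whatever its TV1 score. The simulation does not model such a cluster of low scores. At rho = 0.3, power rises by only about 4 points. This stands.

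The 24-per-arm figure borrows its loss rate from the three-group plan. Withdrawal counts as EOT, and section 5.2 asks for TV5 assessments at withdrawal, so many who stop early would still have a score. The 30-per-arm figures are therefore the main ones.

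Three stronger readings are tempting, and the documents support none of them:
- **That the PWAT comparison is biased, or that TV1 imbalance passes into it in full.** Randomisation makes imbalance a matter of chance, and only about rho times it carries over. Allocation is covariate-adaptive (section 10.3). Its covariates are not named, so it may or may not help balance PWAT.
- **That a reported PWAT estimate is distorted.** Section 10.12.1 specifies a test and no effect estimate.
- **That PWAT is nearly the only blinded between-arm outcome.** LHR and weekly LHR are also read by the blinded expert and compared between groups.

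**Conclusion.** The point holds as an avoidable loss of efficiency on one secondary endpoint. Its direction follows from the design: a pre-randomisation PWAT score exists for the patients being compared, and the stated test leaves it out. Its size is uncertain because rho and the 0.6 SD effect are assumptions, as is equal allocation. Over the range shown, the unadjusted test forgoes about 4 to 26 percentage points of power at 30 per arm (62.8% against 66.8% to 89.2%). The change is worth making because it uses only data already collected. No conclusion about the primary endpoint depends on it.

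**What to change.** In section 10.12.1, and in the SAP before database lock, specify the between-arm PWAT analysis as a rank ANCOVA: ranked EOT PWAT as response, treatment arm as factor, ranked TV1 PWAT as covariate. Keep the unadjusted Mann-Whitney test on EOT scores as a sensitivity analysis. Do not substitute a simple change from TV1.

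A proportional-odds model with TV1 PWAT as covariate, or a van Elteren test stratified by TV1 PWAT, would also use the baseline score. Rank ANCOVA stays closest to the plan's non-parametric approach. Whichever is chosen should be named in advance.

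The cost is one sentence in the protocol and one in the SAP. No new visit, image or score is needed.

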2.2 Safety assessment

Safety will be assessed based on incidence of adverse events (AEs), incidence of serious AEs (SAEs), incidence of study treatment related AEs, incidence of investigational device related AEs, ulcer infection, and incidence of pain in the ulcer site (sudden onset of pain or increase in pain during the study treatment).

3 Study Design

This study is designed as a prospective, multicentre, randomised, assessor blinded study designed to compare the efficacy including participant reported outcomes of two different gekoTM treatment durations in conjunction with SC, with each other and with SC alone, in the treatment of patients with venous leg ulcers. There will therefore be two arms in the study consisting of: 1) participants randomised to receiving SC only; 2) participants randomised to receiving SC, and gekoTM 12 hours daily.

The standard care therapy in this study is multilayer, multicomponent compression therapy intended for the treatment of VLU. A non-adherent (NA) wound contact dressing and/or an absorbent dressing may be used if required, at the Investigator's discretion in addition to SC. All dressing use and reason for dressing use will be recorded.

Multiple multilayer, multicomponent compression bandaging systems delivering levels of compression and with clinical data to support their use are commercially available. The compression bandaging system of choice based on local best practice will be used. Moreover, this will prevent any problems around consistency of method of application of compression.

The study will be a multinational, multicentre study with study centres in the UK and Europe

The study will have three phases: a four-week Run-in Phase, a four-week Treatment Phase and a twelve-week follow-up phase. A schematic picture of the study flow is provided below in Figure 1.

[figure not shown]

Figure 1: Study Schedule

At or up to 21 days before the first Run-in Phase Visit (RV1), the Investigator or suitably qualified designee will, prior to the performance of any protocol-specific procedure, obtain written informed consent from the patient.

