3.1 Study Population

3.1.1 Number of Participants

A total of 60 patients will be randomised into the study

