10.3 Randomisation

This is a multi-centre randomised clinical study. Participants will be allocated to treatment groups using Adaptive Covariate Randomisation using an on-line randomisation tool (29).

The randomisation will be applied centrally across the sites.

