10.5.1 Procedure for Interim Analysis

The data to be used in the interim analysis and the treatment assignment of each randomised subject will be given to the statistician. Using this data, the independent statistician will calculate the following metrics for the primary end point:

1. Mean and standard deviation of LHR in each group.
2. The dropout rate at the time of the Interim Analysis, IA
3. The statistical power of the trial at the time of the IA (using a conditional power approach).
 - a. If the statistical power is larger than 50%, then the sample size will be adjusted upward and no Type I error rate adjustment will be made to the final analysis.
 - b. If the statistical power is less than 50%, the Type I error rate will be inflated and statistical adjustment will be made to the final analysis if the decision to increase the sample size is made. That is, the observed p-value, as well as the point estimate of the response rates, and the 95% CIs will be based on:

$$p\text{-value} = 2 * \{1 - T_2(n_1+n_2 - 1) (|z_1 + z_2|/\sqrt{2})\},$$

Healing rate for each treatment group: $\hat{S} = (\sqrt{n_1} \times \hat{S}_1 + \sqrt{n_2} \times \hat{S}_2) / (\sqrt{n_1} + \sqrt{n_2})$,

95% Confidence Intervals = $(\hat{S} - 2 \text{ta}/2:2(n_1+n_2 - 1)\sigma, \hat{S} + 2 \text{ta}/2:2(n_1+n_2 - 1)\sigma)$

where n_1 is the sample size in the treatment group before interim analysis and n_2 is the sample size in treatment group after the interim analysis; $T_2(n_1+n_2 - 1)$ (.) is t distribution with $2(n_1+n_2-1)$ degrees of freedom. The \hat{S}_1 is the healing rate of the n_1 observation before the interim analysis and \hat{S}_2 is the healing rate of the n_2 observation after the interim analysis. The $(\sqrt{n_1} + \sqrt{n_2})\sigma$ is the observed pooled standard deviation before and after the interim analysis.

4. Using the observed metrics above, along with Type I Error Rate of 0.05, the sample size will be re-calculated and the independent statistician will provide the following to the sponsor and the statistician responsible for the trial:
 - a. Re-estimation of sample size using the observed rate of healing and dropout rate
 - b. The difference in percentage of healed subjects
 - c. The healing rate in Treatment arms
 - d. The healing rate in the Control arm
 - e. The power used in calculating the new sample size

No other information will be shared with the sponsor or the statistician responsible for this trial.

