10.5.2 Results of Interim Analysis

The new sample size calculation is:

Based on a pair-wise comparison of geko™ 12h run-in vs treatment:

From the interim data, there is a mean difference of 0.58 mm/week between run-in and treatment and a standard deviation of 0.97 mm/week.

Assuming requirements of 80% power and $p=0.05$ (2-sided) 25 subjects would be needed in the geko™ 12H group. (30)

Little benefit is foreseen in continuing the geko™ 6h group, as statistical significance is not expected at the projected number of subjects in this trial.

From the results of the Interim Analysis the new Treatment Groups are:

Group	Description
SC	Standard care (multilayer, multicomponent compression intended for the treatment of VLU)
geko 12h	geko™ version XW, W-3 or variant (12 h daily neuro-stimulation) and SC

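### Fisher's exact test for incidence of healing is valid but conservative at this size; Boschloo's exact test, ordered by the two-sided Fisher p-value, would be a cheap gain in power on a secondary endpoint

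*Combined protocol and SAP*

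**What the plan says.** Section 10.7.2 lists among the secondary endpoints "Incidence of healing at end of study, as determined by the Investigator". Section 2.1.2 places the same endpoint at end of treatment, which is four weeks after randomisation at the latest. The test is given in Section 10.12.1: "Incidence of healing shall be compared between groups using Fisher's exact test". No expected healing rates, power or sample size are given for this endpoint.

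On numbers, Section 3.1.1 says "A total of 60 patients will be randomised into the study", and Section 3 describes two arms, standard care (SC) alone and SC plus geko 12 hours daily. Section 10.3 gives the method of allocation ("Participants will be allocated to treatment groups using Adaptive Covariate Randomisation using an on-line randomisation tool") but no ratio.

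On the level, Section 10.12 says "All statistical tests will be two-sided and a 0.05% significance level maintained throughout the analyses", whereas Section 10.5.1 works "along with Type I Error Rate of 0.05, the sample size will be re-calculated" and Section 10.5.2 also uses a two-sided 0.05.

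Under Section 10.11, patients who withdraw during treatment count as treatment failures, so denominators should stay close to the numbers randomised. Patients with no post-randomisation wound assessment still drop out of the ITT population under Section 10.10.1.

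**The concern.** Fisher's test conditions on the total number healed. With about 30 patients per arm and few ulcers closing, the conditional distribution has only a handful of possible values, so the attainable level often lies well below the nominal 5%. The unused error rate is lost power.

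Few closures in four weeks is a reasonable expectation: the only background figure in the documents is about 45% healed at 12 weeks under optimal compression (Section 1.3). Complete closure is also a direct clinical outcome. A real difference could be reported as non-significant because of the choice between two exact tests. At 30/30, 5 healed against 0 gives a Fisher p-value of 0.052 and a Boschloo p-value of 0.027; 7 against 1 gives the same pair of values.

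**Working it through.** **The plan's own sample size.** The documents give no figure for healing, only the paired calculation in Section 10.5.2: "there is a mean difference of 0.58 mm/week between run-in and treatment and a standard deviation of 0.97 mm/week".
- Normal formula: n = ((1.960 + 0.842) × 0.97 / 0.58)² = 21.95, so 22.
- Noncentral t: n = 24 has power 80.1% and n = 25 has 81.8%. The stated 25 is reproduced to within one patient.
- Section 10.2 inflates 35 to 42, a factor of 1.2. The same factor gives 25 × 1.2 = 30, and 2 × 30 = 60. Thirty per arm is therefore a reasonable reading of the total, but it is inferred.

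**Method.** For arms of n₁ and n₂, every table (a healed of n₁, b healed of n₂) is enumerated.
- Fisher rejects when its two-sided p ≤ 0.05.
- True size at a common healing rate π is the sum, over rejected tables, of Bin(a; n₁, π) × Bin(b; n₂, π). It is maximised over π from 0.001 to 0.999.
- Boschloo rejects when the two-sided Fisher p ≤ c, where c is the largest cut-off whose maximum size is at most 5%. Fisher's own size is below 5%, so c is at least 0.05 and Boschloo's region contains Fisher's.
- Power is the same sum with different rates in the two arms.

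**Size at 30/30.** Fisher's maximum is 2.74%, at π = 0.50. It is 0.15% at π = 5%, 0.94% at 10% and 2.2% at 20%. Boschloo has c = 0.0692, adds 32 tables and has maximum size 4.69% (0.7% at π = 5%, 2.3% at 10%).

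**Fisher's maximum size at other splits.** 29/31: 3.90%. 28/32: 3.68%. 27/33: 3.76%. 30/25: 3.72%. 35/25: 3.6%. 20/40: 3.7%. 25/25: 3.28%. 24/24: 2.9%. The 30/30 figure is the lowest of those checked.

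**Power (%), Fisher → Boschloo, two-sided 5%.** Healing rates are assumed.

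| SC vs geko | 30/30 | 29 SC/31 geko | 25 SC/30 geko | 32 SC/28 geko | 30 SC/25 geko |
|---|---|---|---|---|---|
| 3% vs 20% | 34.1 → 46.9 | 37.7 → 50.6 | 36.2 → 50.8 | 54.1 → 54.1 | 47.0 → 47.0 |
| 5% vs 20% | 24.1 → 33.5 | 27.3 → 37.0 | 26.1 → 38.2 | 38.8 → 38.8 | 32.9 → 32.9 |
| 5% vs 25% | 43.6 → 52.7 | 47.9 → 56.8 | 44.9 → 57.4 | 56.9 → 57.0 | 49.8 → 49.8 |
| 10% vs 35% | 54.5 → 59.4 | 59.0 → 64.6 | 53.3 → 61.7 | 61.3 → 62.1 | 55.1 → 55.2 |
| 20% vs 50% | 59.6 → 67.1 | 65.1 → 69.2 | 60.8 → 65.9 | 64.3 → 70.4 | 60.8 → 62.4 |

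At 30/30 the gain over these pairs is about 5 to 13 points; at 10% vs 40% it is a little lower (70.5 → 74.3). With 31 SC/29 geko, 5% vs 20% gains under 1 point.

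**Software.** scipy's two-sided Boschloo p-value is twice the smaller one-sided value, which is a different test when arms are unequal. At 29/31, 4/29 against 0/31 gives Fisher 0.0487 and scipy 0.0549; 6/29 against 1/31 gives 0.0490 and 0.0540. With the two-sided Fisher p-value as ordering statistic, both tables have p = 0.039. At 30/30 the two versions agree on the examples above.

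**The printed level.** Taking 0.05% literally at 30/30, the maximum sizes are 0.021% (Fisher) and 0.047% (Boschloo). The direction is the same.

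**The case against.** The strongest reply is that nothing here is wrong. Fisher's test is valid and prespecified, the endpoint is secondary and unpowered, and no decision rule in the documents depends on its p-value. That stands. A reader might infer from the low true size that the planned test is an error; the documents do not support this, because a conservative test still controls type I error.

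A reader might also take 2.7% as the test's true error rate in this trial. It applies only to an exact 30/30 split. Adaptive covariate allocation does not force equality, and the documents do not say whether the 60 include patients already randomised to the dropped 6-hour arm. At nearby unequal splits the maximum is 3.7% to 3.9%, and the power gain can vanish. This limits the size of the point but not its direction, since power never falls.

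Finally, it is tempting to call the change free. Boschloo's test holds its level unconditionally, not given the observed total healed. With 5 healed in total at 30/30, rejecting a 5–0 result has a conditional level of 5.2%, and at the cut-off itself the conditional level is 6.9%. This is a genuine though small downside. It does not decide the matter, because the total healed is not fixed by the design and the unconditional error rate is the relevant one here.

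**Conclusion.** The point holds as a modest efficiency improvement. At a two-sided 5% level, Fisher's test has a maximum true size of 2.7% at 30/30 and 3.7% to 3.9% at 29/31, 28/32 or 30/25. Boschloo's test with the stated ordering stays at or below 5%. It adds about 5 to 13 points of power at 30/30 over the five rate pairs tabulated, and 0 to about 15 points at the other splits checked.

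This rests on three assumptions: arms of roughly 30, which are inferred; healing rates that the documents do not give; and 5% as the intended level, despite the 0.05% printed in Section 10.12. The numbers do not show that any particular gain will be realised in this trial, and they do not touch the primary linear healing rate analysis.

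**What to change.** First reconcile the significance level in Section 10.12 with Section 10.5. Then, in Section 10.12.1 and the SAP, and before database lock and unblinding:
- replace Fisher's test for incidence of healing with Boschloo's exact unconditional test, two-sided at 5%, with the two-sided Fisher p-value as ordering statistic;
- name software, or a short validated program, that uses this ordering, and rule out doubling the smaller one-sided p-value;
- report the difference in healing proportions with an exact unconditional 95% confidence interval;
- state that type I error is controlled unconditionally.

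The cost is a few lines of text and a check of the program. No further patients or data are needed. Section 10.12 already leaves detailed methods to a SAP approved before lock, so there is a natural place for the change.
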